AUC	Area Under Curve
BG	Blood Glucose
CEC	Clinical Events Committee
CFR	Code of Federal Regulations
CGM	Continuous Glucose Monitoring
CGMS	Continuous Glucose Monitoring System
CIP	Clinical Investigation Plan
CSII	Continuous Subcutaneous Insulin Infusion
DKA	Diabetic Ketoacidosis
DMC	Data Monitoring Committee
DQoL	Diabetes Quality of Life questionnaire
DTSQ	Diabetes Treatment Satisfaction Questionnaire
DTSQc	Change Version of DTSQs
DTSQs	Status Version of DTSQs
EC	Ethics Committee
eCRF	Electronic Case Report Form
EIS	Electrochemical Impedance Spectroscopy
EMEA	Europe Middle East Africa
EOS	End of Study
ER	Emergency Room
FDA	United States Food and Drug Administration
FGM	Flash Glucose Monitoring

Abbreviation	Definition
GCP	Good Clinical Practice
HbA1c	Glycosylated hemoglobin
HFS	Hypoglycemia Fear Survey
HL	HelpLine
ICHOM	International Consortium for Health Outcomes Measurement
ICU	Intensive Care Unit
IFU	Instructions for Use
ICMJE	International Committee of Medical Journal Editors
IRB	Institutional Review Board
ITT	Intent to Treat
IV	Intravenous
MAGE	Mean Amplitude of Glycemic Excursions
MDI	Multiple Daily Injections
MDRD	Modification of Diet in Renal Disease (equation)
NGSP	National Glycohemoglobin Standardization Program
OC-RDC	Oracle Clinical Remote Data Capture
PC	Personal Computer
PIC	Patient Information and Informed Consent Form
QC	Quality Control
RA	Regulatory Authority
RF	Radio Frequency
RT	Real-Time
SAE	Serious Adverse Event
SADE	Serious Adverse Device Events
SAP	Sensor Augmented Pump
SG	Sensor Glucose
SMBG	Self-Monitoring of Blood Glucose
T1DM	Type 1 Diabetes Mellitus
TDD	Total Daily Dose
TIR	Time in Range
TLS	Transport Layer Security
USADE	Unanticipated Serious Adverse Device Effect

3. Introduction

3.1 Background

In patients with insulin dependent diabetes mellitus, glycemic control is influenced by numerous factors, such as insulin dosage, insulin absorption, timing, physiological/ lifestyle factors such as exercise, food intake, hormones and illness. These factors may contribute to significant variability in insulin requirements, which makes self-management of type 1 diabetes challenging.

Patients who are using continuous glucose monitoring, including sensor-augmented pump therapy, experience improvements in glycemic control (Bergenstal, 2010; Battelino, 2012). Advanced features of sensor-augmented pump therapy are now being used in clinical practice; these include automatic suspension of insulin delivery when a pre-set glucose threshold is reached (suspend on low) or is predicted to be reached (suspend before low). Both approaches have shown that a significant reduction in the risk and burden of hypoglycemia can be achieved, especially in patients who are prone to experiencing hypoglycemia (Bergenstal, 2013; Bosi, 2019).

Parallel to these approaches to mitigate the risk of hypoglycemia, more progressive advancements in technology can link insulin delivery directly to glucose levels. Closed-loop insulin delivery is different from conventional pump therapy and low glucose management technology, because it uses a control algorithm to automatically adjust insulin delivery based on subcutaneous sensor data to improve diabetes management. Manual meal-time announcement and prandial insulin boluses still need to be carried out by patients in order to overcome the delay in insulin action of currently available insulin analogues administered subcutaneously. The 'hybrid' closed-loop approach is in contrast to a 'fully' closed-loop approach, in which user input to the control algorithm related to meals would no longer be required.

One arm of the study will assess the MiniMed™ 670G running in advanced hybrid closed loop (AHCL) mode. The MiniMed™ 670G hybrid closed loop system is currently in commercial distribution in the United States and in an increasing number of European countries. Real world data from the MiniMed™ 670G in the United States has documented safety and efficacy in adults and children (Stone, 2018). There have, however, been further advancements to the hybrid close loop proportional integrative derivative (PID) algorithm model that seek to improve functionality and efficacy based on retrospective analysis of data from the MiniMed™ 670G insulin pump, using a modified proportional integrative derivative model, with insulin feedback and additional safety features. These enhancements intended to maximize time spent in hybrid closed-loop operation, in order to further improve glucose control and overall user satisfaction. Advancement have been implemented in the new system with the algorithm version 4.0, such as automatic correction bolusing, sensor glucose based meal bolusing, automatic calibrations of Blood Glucose (BG) measurements transmitted to the pump and a variable target for automatic basal deliveries, all of which are intended to contribute to a reduction of unnecessary Auto Mode exits, which will consequently increase time in euglycemic range and overall user satisfaction.

The advanced algorithm receives continuous glucose monitoring (CGM) data every 5 minutes, and a “basal rate” insulin delivery is computed and adjusted every five minutes. Therefore, standard “basal” insulin that is pre-programmed in regular insulin pump therapy is replaced by the algorithm derived insulin delivery (given as a micro-bolus every 5 minutes).

Meals will be announced, and sensor glucose based insulin bolus for a meal will be delivered according to the individualised patient carbohydrate ratio and insulin sensitivity factor.

In 2018, [name] conducted a feasibility study exploring the function of an updated iteration of the MiniMed™ 670G in Australian adults. Overall, the study showed a high percentage of time in Auto Mode with reduced Auto Mode exits per week. Overall, the subjects spent 83.8% of time in range (70 mg/dL to 180 mg/dL) with a mean sensor glucose of 125.2 mg/dL.

In 2018, [name] conducted another feasibility study to further assess the safety and efficacy of the AHCL algorithm in adolescents and young adults in Israel, in order to refine the algorithm and assure the safety of the system, prior to entering into the planned pivotal studies to obtain market access of the AHCL algorithm in the MiniMed™ 670G System.

Following these feasibility studies, several studies are currently ongoing on AHCL MiniMed™ 670G System to demonstrate the safety and effectiveness on the AHCL MiniMed™ 670G System version 4.0 (**Table 1: AHCL**). Nevertheless, additional clinical evidence is required to support the available efficacy and safety data with additional long-term data of the AHCL system in comparison with the current standard of care for Type 1 Diabetes.

Across the world, the majority of Type 1 Diabetes patients requiring insulin are treated with Multiple Daily Injection (MDI) therapy. While a growing population have access to diabetes technology through Flash Glucose Monitoring (FGM) or Continuous Glucose Monitoring (CGM) in the EMEA region, a large proportion of insulin requiring patients with Type 1 Diabetes on MDI therapy with FGM or CGM still have sub-optimally controlled diabetes management with a HbA1c > 8.0 % (64 mmol/mol). Additional long-term efficacy and cost-effective data will be needed to further support market access and adoption of AHCL therapy for those patients who are not well controlled with the current standard of care for Type 1 diabetes patients requiring insulin.

Table 1: AHCL clinical studies

Study	Design	Primary Endpoints	Status
[name]	7days hotel/clinic + 3 weeks at home, single arm, with 12 subjects >18 years old with Type 1 Diabetes in Australia	Feasibility	Completed
[name]	1 week, single arm with 12 subjects >14-40 years old with Type 1 Diabetes in Israel	Feasibility	Completed
[name]	4 weeks, randomized vs PLGM, two-sequence cross-over with 60 subjects >7 – 70 years old with Type 1 Diabetes in New Zealand	Safety and Efficacy, Time in Range 3.9-10 mmol/L and Time in Hyperglycemia >10 mmol/L	Completed
Medtronic Pivotal study	12 weeks, single arm in 250 subjects > 7 years old with Type 1 in United States	Safety, HbA1c	Expected completion 2020
FLAIR Study	12 weeks, randomized vs 670G, two-sequence crossover multi-center study in 112 subjects 14-30 years old with Type 1 Diabetes in United States, Germany, Slovenia and Israel	Efficacy and Safety, Time in Hyperglycemia >10 mmol/L and Time in Hypoglycemia 3.0 mmol/L	Completed 2020
Medtronic ADAPT study	2 weeks run-in + 6-month randomized phase AHCL vs MDI, single crossover + 6-month continuation AHCL with 124 subjects > 18 years old with Type 1 Diabetes in France, UK and Germany	Efficacy and Safety, HbA1c	Expected completion 2021

This Statistical Analysis Plan (SAP) will be used to support analysis of the continuation phase of the ADAPT study. The Statistical Analysis Plan has been designed to document, before data is analyzed, the planned analyses for the final report. This SAP does not limit the analysis in reports, and additional analyses of the study data beyond this plan might be conducted. However, this document provides the basis for the statistical sections of the final report. Analyses not planned in the SAP and incorporated into the final report will be referred to as “not-prespecified”. Further, in case any analyses will be done differently than planned in the CIP or SAP, an explanation will be provided in the final report.

4. Continuation Phase Objectives

All analysis in this document is exploratory. Cohort A and Cohort B will be analysed independently.

4.1.1 Objective for Control Group

The primary objective for control group is to evaluate the superiority on glycemic control of the AHCL system in continuation phase versus MDI therapy in study period.

[figure not shown]
4.1.2 Objective for Treatment Group

The primary objective is to confirm the long-term benefits of AHCL therapy. The non-inferiority on glycemic control of the AHCL system in continuation phase versus in study period will be tested.

5. Investigation Plan

This study is a pre-market, multi-center, prospective, open label, adaptative, confirmatory, randomized controlled trial in insulin-requiring adult subjects with type 1 diabetes on MDI therapy. The study period for each subject will be approximately 13 months.

Figure 1: Study Design

The study consists of two separate cohorts, Cohort A with subjects on MDI + FGM (confirmatory part of the study) and Cohort B with Subjects on MDI + Real-Time CGM (exploratory part of the study). Each cohort will have a separate randomization.

5.1 Duration

Overall study duration from first subject enrollment until the last subject exit is expected to last approximatively 25 months, including an estimated 6-month site activation period, 6-month enrollment period, and a 13-month follow-up period for each subject.

Each subject will enter a run-in phase of approximately 2 weeks, followed by a study phase of 6 months, then a 6-month continuation phase.

5.2 Randomization

If subjects meet the inclusion and exclusion criteria, as well as all the following criteria assessed at the end of the run-in period, they may continue to participate in the study phase:

1. Subject has worn the sensor with blinded transmitter during the run-in period adequately, per investigator judgment.
2. Subject has shown acceptable tolerance to sensor wear, per investigator judgment.
3. CareLink data shows subject performed ≥ 2 finger stick blood glucose measurements daily, as determined by CareLink data upload as the mean number of SMBG/day over the past 14 days.
4. Subject has shown compliance with study procedures, per investigator judgment.

Subjects in each cohort will be randomized into 2 arms at the end of the run-in phase:

Cohort A (confirmatory): Subjects on **MDI + FGM** will be randomized into:

- Treatment Arm: Start AHCL (and stop FGM at visit 6A)
- Control Arm: Continue MDI + FGM

Cohort B (exploratory): Subjects on **MDI + Real-Time CGM** will be randomized into:

- Treatment Arm: Start AHCL (and stop CGM at visit 6A)
- Control Arm: Continue MDI + CGM

Each cohort will have a separate randomization.

6. Determination of Sample Size

Subjects entered the continuation phase after completed the study period. All subjects with data in the continuation phase will be included in the analysis. No power analysis has been done for this exploratory phase of the study. All analysis in this document is exploratory.

6.1 Sample Size for Study period

Subjects will be enrolled in the study at up to 20 investigational centers in EMEA (see Clinical Investigation Plan section 6.2).

In Cohort A, approximately 84 MDI + FGM subjects will be enrolled to achieve approximately 70 subjects randomized and 64 subjects completing the 6-month study phase.

In addition, in Cohort B approximately 40 MDI + RT-CGM subjects will be enrolled to achieve 34 subjects randomized and 30 subjects completing the 6-month study phase.

6.2 Sample Size Considerations for Study Period

For Cohort A (MDI+FGM), the sample size calculation was performed based on the following assumptions: alpha=0.05, power=80%, 0.7 standard deviation and 0.5 reduction in mean change of HbA1c in the treatment arm, as compared to the control arm, which is the minimum clinically meaning difference. The standard deviation was based on the *Eurythmics study* (Hermanides, 2011) comparing SAP therapy (Treatment arm) vs MDI (control arm) with a pooled standard deviation of 0.83.

Based on these assumptions, the minimum sample size required is 64 subjects (32 in each arm) in Cohort A comparing AHCL with MDI + FGM subjects.

The following drop-out assumptions have been taken into account, based on experience with previous studies: At screening: 10%; After run-in: 5%; During 6-month follow-up: 7.5%.

Incorporating these drop-out rates, a total of 84 subjects need to be screened in Cohort A (AHCL vs MDI+FGM) in order to have 74 subjects starting the run-in phase, 70 subjects randomized to start the treatment phase and 64 subjects to complete the study phase (6 months). To minimize imbalance in the number of subjects across sites, a minimum of 4 and a maximum of 20 subjects of the cohort should be randomized at each site, with the current sample size.

For the exploratory analysis in Cohort B, comparing MDI + CGM versus AHCL, 30 subjects will be required for analysis. Incorporating the expected dropout rates, a total of 40 subjects need to be screened, in order to have 36 subjects starting the run-in phase, 34 subjects randomized to start the treatment phase and 30 subjects to complete the study. Subjects will be randomized in a 1:1 ratio to the 2 arms.

7. Statistical Methods

The methods in this section are applicable to cohort A and cohort B in continuation phase. The analysis is focused on comparing the therapy outcomes of control group between the study period and continuation phase in cohort A. Similar analysis for treatment group will be conducted as well. These methods are also applicable to cohort B.

7.1 Study Subjects

7.1.1 Disposition of Subjects

The number of subjects entered, completed, and early terminated in the continuation phase for each group and both cohorts will be presented. The reasons for discontinuing prior to study completion will be summarized.

7.1.2 Clinical Investigation Plan (CIP) Deviations

All protocol deviations will be presented in the listings.

7.1.3 Analysis Sets

7.1.3.1 Efficacy analysis set

For the primary, secondary and ancillary endpoints efficacy analyses will be performed in the Intent to Treat (ITT) basis. The ITT set will be composed of all subjects who entered the continuation phase.

7.1.3.3 Safety set

Safety analysis will include all subjects entered continuation phase and safety data will be presented. Any AE and SAE occurring after the date of visit 9 to the date of Visit 13 will be reported as happening in the continuation phase and will be reported according to the randomization arm that the subject was assigned. For comparison of safety in the two periods, the safety set is composed of all subjects in study period and continuation phase and assessed and analyzed as members of each period.

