
Treatment Arm	Control Arm
	
▪ Advise subject to perform at least 4 fingerstick blood glucose measurements per day with the study meter.▪ Provide Blinded CGM Diary to Subject▪ Dispense supplies to subject (indicative quantity for 3 weeks):
○ 1 CONTOUR NEXT LINK 2.4 (subject uses same meter as dispensed previously)○ 80 Strips○ 2 Guardian Link 3 Transmitters (1 is back-up)○ 4 sensors (2 are back-up)○ Charger○ One-press serter

Treatment Arm	Control Arm

Visit 9: End of Study Phase [Visit 8 + 14 days (Window + 7 days)]
 
Site staff will call the subject to:
 
▪ Ensure CareLink upload was done / Advise subject to perform weekly CareLink uploads▪ Review AHCL therapy / Adjust settings▪ Review adverse event or device deficiency, if any.▪ Plan the next visits until Visit 13.	
Visit 9: End of Study Phase / Pump Start [Visit 8 + 14 days (Window + 7 days)]
 
This visit can be done remotely or onsite.
 
If the Visit 9 is conducted remotely, the subject will return the devices dispensed at Visit 8 via post-mail/courier, using the provided shipping box. Upon receipt of the supplies at the site, site staff will conduct Visit 9.
 
▪ Collect/Receive from the subject:
○ 1 Blinded CGM Diary○ 2 Guardian Link 3 Transmitters○ 1 CONTOUR NEXT LINK 2.4 meter○ 1 Charger○ One-press serter○ Unused Sensors▪ Upload data from the Meter in CareLink using correct Subject ID (327-XXX-XXX).▪ Upload data of Transmitter using the Download utility. Make sure to use correct file name (Subject ID_Visit9_DATE). Refer to Blinded CGM Instructions for more details.▪ Record % of use of CGM and average number of scans and % sensor readings for FGM over the previous 2 weeks (based on downloaded and printed report). If the visit is conducted remotely, the site can call the subject and document this in medical chart or subject can share the report via email.▪ Review adverse event or device deficiency, if any.▪ Site staff will train subject on the AHCL insulin pump and subject starts using the insulin pump.▪ Set-up subject CareLink Account.▪ Train subject to perform weekly CareLink uploads.

Treatment Arm	Control Arm

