9.4. CONTINUATION PHASE

Treatment Arm	Control Arm

Visit 10 Follow-up call [Visit 8 + 1 month (Window \pm 7 days)]
 
Site staff will call the subject to:
 
▪ Ensure CareLink upload was done / Advise subject to perform weekly CareLink uploads.▪ Review AHCL therapy / Adjust settings.▪ Review adverse event or device deficiency, if any.	
Visit 10 Training Follow-Up [Visit 9 + 3 days (Window \pm 1 day)]
 
This visit can be done remotely or onsite.
 
Subject will be trained on infusion set change and receive additional retraining on pump, as needed.
 
Site staff will:
 
▪ Review AHCL therapy / Adjust settings.▪ Review adverse event or device deficiency, if any. 
If the visit is conducted onsite, site staff will additionally:
 
▪ Upload AHCL into CareLink. Use correct Subject ID (327-XXX-XXX).

Visit 11 Follow-up call [Visit 10 + 1 month (Window \pm 7 days)]
 
Site staff will call the subject to:
 
▪ Ensure CareLink upload was done / Advise subject to perform weekly CareLink uploads.▪ Review AHCL therapy / Adjust settings.▪ Review adverse event or device deficiency, if any.	
Visit 11A CGM Start [Visit 9 + 7 days (Window + 7 days)]
 
This visit can be done remotely or onsite.
 
▪ Upload AHCL into CareLink if visit is onsite. Use correct Subject ID (327-XXX-XXX)▪ Ensure CareLink upload was done / Advise subject to perform weekly CareLink uploads.▪ Review AHCL therapy / Adjust settings.▪ Retrain subject on Pump as needed.▪ Start CGM with AHCL (Manual Mode) and subject stops FGM/RT-CGM.▪ Review adverse event or device deficiency, if any. 
If Visit is planned to be conducted remotely, site staff can dispense supplies to subject at a previous visit or ship those to subject prior to the visit
 
▪ Dispense/ship supplies to subject (indicative quantity for 3 months):
○ 1 Guardian Link 3 Transmitter kit○ 20 sensors○ 750 strips

Treatment Arm	Control Arm
	
○ 30 Infusion sets (3 boxes of 10)○ 30 Reservoirs (3 boxes of 10)○ 12 AA batteries (3 packs of 4)

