Height and weight									X	X
HbA1c (Central lab)									X	X
Pump training	C		C	C	C	C	C			
CGM training			C	C	C	C	C			
Auto Mode Training/Start				C						
CareLink upload at site	C°		C	C°	C°	C°	C°	X	X	X
CareLink upload by subject	T	T	C	C	C	C	C	X	X	X
Review therapy / Adjust settings	X	T	C	C	C	C	C	X		
HFS questionnaire									X	X
DTSQs questionnaire									X	X
DTSQc questionnaire									X	X
DQoL questionnaire									X	X
AEs and Deficiencies										
								Reported upon awareness		
Study deviations										
								Reported upon awareness		
Device Accountability	X		C						X	
Distribution supplies	X		C	C°	C°	C°		X		
Return supplies									X	X

X = both arms; T = Treatment arm; C = Control arm ; O / ° = Optional FU = Follow Up

³Early Termination visit should be performed at any time if patient withdraws after randomization (Visit 4) and before the end of the study (Visit 13).

⁴In pandemic situation, visit can be conducted remotely.

Medtronic Business Restricted

This document is electronically controlled

056-F275, v B Clinical Investigation Plan Template

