11.1. Adverse Events

Throughout the course of the study, investigational centers will make all efforts to remain alert to possible reportable adverse events (AEs) or untoward findings. All adverse events identified from the point of enrollment until the subject's exit from the study will be reported to the sponsor and documented on the Adverse Event eCRF and in the subject's medical records. The study personnel will elicit reports of adverse events (AEs) from the subject at each visit (including phone calls) documenting the medical diagnosis, date of event start and end, causality (relationship to device or procedure), treatment, outcome, and description that includes the details of the event.

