7.10 Safety Evaluation

7.10.1 Number of severe hypoglycemic events

Severe Hypoglycemia is an event requiring assistance of another person due to altered consciousness to actively administer carbohydrate, glucagon, or other resuscitative actions. This means that the subject was impaired cognitively to the point that he/she was unable to treat him or her self, was unable to verbalize his or her needs, and was incoherent, disoriented and/or combative. These episodes may be associated with sufficient neuroglycopenia to induce seizure or coma. Plasma glucose measurements may not be available during such an event, but neurological recovery attributable to the restoration of plasma glucose to normal is considered sufficient evidence that the event was induced by a low plasma glucose concentration. Total number of severe hypoglycemic events reported in the eCRF, during Continuation Phase will be reported. Total number of severe hypoglycemic events during the Continuation Phase (from date of Visit 9 to date of Visit 13) will be reported by treatment arm. The number of severe hypoglycemic events per year will be computed for each subject based on the entire continuation phase duration (happening after Visit 10 to and including Visit 13). If a subject i is followed up for x_i years and the number of observed severe hypoglycemic events during that follow up is m_i , the number of severe hypoglycemic events per year (SHEyear) for patient i will be estimated as:

$$\frac{m_i}{x_i}$$

Annualized crude incidence rates will be expressed as number of severe hypoglycemic events per 100 patients' year and will be calculated as:

$$\frac{\sum_{i=1}^n m_i}{\sum_{i=1}^n x_i} \times 100$$

where $i=1, 2, \dots, n$ and n total number of subjects.

The number of severe hypoglycemic events per 100 patients' year during the study phase will be reported by study arm.

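### The SAP uses three different continuation-phase safety windows, and none gives a closing date for subjects who leave before Visit 13

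*SAP*

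**What the plan says.** Three rules in the SAP place safety events in the continuation phase.

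- **AEs and SAEs** (SAP 7.1.3.3): the rule for this phase is "Any AE and SAE occurring after the date of visit 9 to the date of Visit 13 will be reported as happening". The same section puts every subject who entered that phase into the safety set and plans a comparison of safety between the two periods.
- **Severe hypoglycaemia total** (SAP 7.10.1): the number of "severe hypoglycemic events during the Continuation Phase (from date of Visit 9 to date of Visit 13") is reported by arm.
- **Severe hypoglycaemia rate** (SAP 7.10.1): the yearly rate is said to rest on the whole continuation phase, but a parenthesis limits it to events later than Visit 10, up to and including Visit 13. SAP 7.10.2 takes its ketoacidosis rate from the same method.

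For the control arm, protocol 9.3 heads the visit "Visit 9: End of Study Phase / Pump Start [Visit 8 + 14 days (Window + 7 days") and instructs: "Site staff will train subject on the AHCL insulin pump and subject starts using the insulin pump". About a week later, at Visit 11A (protocol 9.4), the instruction is "Start CGM with AHCL (Manual Mode) and subject stops FGM/RT-CGM".

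For subjects who withdraw, the note to protocol Table 6 says that an Early Termination "visit should be performed at any time if patient withdraws after randomization (Visit 4) and before the end of the study (Visit 13"). Protocol 9.7 treats Visit 13 and early termination as alternative exits. Protocol 11.1 sets the collection period: "All adverse events identified from the point of enrollment until the subject's exit from the study will be reported". SAP 7.1.1 expects such exits, since it tabulates "The number of subjects entered, completed, and early terminated in the continuation phase".

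**The concern.** The SAP should count an event in the same phase wherever it is reported. Here the total and the rate for severe hypoglycaemia can rest on different events, and both can disagree with the SAE count. For the control arm the period comparison is MDI against AHCL, so the boundary at Visit 9 decides which therapy an event is reported under. The closing boundary matters for anyone who leaves early: they remain among the subjects analysed, but the SAP does not say up to what date their events count. SAP 7.10.3 does not settle it, because it names only the run-in and study phase. That leaves 7.1.3.3 as the only rule placing SAEs in the continuation phase.

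**Working it through.** The plan states no figure on this point, so there is none to reproduce. The check sets the windows side by side and then sizes the gaps.

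**1. The windows**

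| Use | Opens | Closes | Closing date for early leavers |
|---|---|---|---|
| AEs and SAEs, 7.1.3.3 | after the Visit 9 date | Visit 13 | none given |
| Severe hypoglycaemia total, 7.10.1 | on the Visit 9 date | Visit 13 | none given |
| Severe hypoglycaemia rate, 7.10.1 | after Visit 10 | Visit 13 | none given (person-time is subject-specific, but its end is not defined) |

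Take a serious severe hypoglycaemic event in a control subject. On the Visit 9 date it is outside the first window, inside the second and outside the third. On the following day it is inside the first two and outside the third.

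**2. Length of the phase** (target dates in protocol 9.3 and 9.4; 1 month = 30.44 days)

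- Control arm, Visit 9 to 11A to 11C to 11E to 12 to 13: 7 + 7 + (1 + 1 + 3) × 30.44 = 166 days. With every visit window at its limit the range is 131 to 214 days.
- Treatment arm: Visit 13 is 6 months after Visit 8, and Visit 9 is 14 days after Visit 8, so 6 × 30.44 − 14 = 169 days.

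**3. Days outside the windows**

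- Visit 9 date, control arm: 1/166 = 0.6% (0.5% to 0.8% over the range above).
- Visit 9 to Visit 10, control arm: 3 days (window 2 to 4), 3/166 = 1.8% (1.2% to 2.4%).
- Visit 9 to Visit 10, treatment arm: Visit 10 is Visit 8 + 1 month, so 30.44 − 14 = 16.4 days and 16.4/168.6 = 9.7%. At the visit windows' limits the gap runs from 30.44 − 7 − 21 = 2.4 days to 30.44 + 7 − 14 = 23.4 days.

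The SAP does not say when the person-time in the rate begins. If it began at Visit 9 while events counted only after Visit 10, a constant event rate would be understated by about 1.8% in the control arm and 9.7% in the treatment arm. If both began after Visit 10, the rate would simply ignore those days.

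**4. Early leavers**

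The documents give no continuation-phase drop-out. Assumptions: the 7.5% six-month study-phase rate (SAP 6.2) applies again, leavers exit halfway on average, and their event rate equals that of stayers.

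- Share of events in leavers = (0.075 × 0.5) / (0.075 × 0.5 + 0.925) = 0.0375/0.9625 = 3.9%.
- At 2.5% drop-out: 0.0125/0.9875 = 1.3%. At 15%: 0.075/0.925 = 8.1%.
- Cohort A control arm, 32 planned completers: 32 × 0.075 = 2.4 subjects without a Visit 13 (0.8 at 2.5%, 4.8 at 15%).

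**The case against.** The strongest reply is that this is loose drafting with small effects in an exploratory plan. Much of that stands.

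- All analyses in this SAP are exploratory, p-values for safety endpoints may not be claimed, and no sample size or power figure depends on these dates.
- A reader might infer that Visit 9 events are charged to MDI. The documents do not say so. This SAP defines no study-period adverse-event window, so such an event could fall in the study period or in neither. The day is also part MDI and part pump use without the study sensor: CGM starts about 7 days later and Auto Mode about 14. In the treatment arm, which is on AHCL on both sides of Visit 9, only the period label is affected.
- A reader might infer that the SAP excludes early leavers' events. It does not order that. Keeping all entrants in the safety set, collecting events to exit, analysing all available data (SAP 7.4) and using subject-specific follow-up all point to keeping them. The loss arises only if a missing Visit 13 date is used as a literal cut-off.
- A reader might infer that the severe hypoglycaemia total and rate close at different points. Both close at Visit 13; they differ at the opening.
- A reader might expect leavers to have more events and so a larger loss. The documents give no event rate for leavers, so the size given here assumes equal rates.
- Protocol 11.1 names event dates and no clock times. Moving the whole Visit 9 date into the continuation phase could therefore count events from before pump start under AHCL.

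None of this removes the three different openings or supplies the missing closing date.

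**Conclusion.** The point holds as an inconsistency and an omission. It does not show a bias in a known direction. SAP 7.1.3.3 and 7.10.1 give three windows that can classify one event differently, and none closes for subjects without a Visit 13. The largest opening gap is the one after Visit 10: nominally about 16 days in the treatment arm and 3 in the control arm. The Visit 9 gap is one control-arm day in about 166. The closing gap puts about 4% of continuation-phase events at risk of omission (1.3% to 8.1% for drop-out of 2.5% to 15%), on the assumptions of halfway exit, equal event rates and a literal cut-off. It should be corrected before the continuation-phase safety tables are produced, although no confirmatory conclusion turns on it.

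**What to change.** Use one interval in SAP 7.1.3.3, 7.10.1 and 7.10.2, for event counts and person-time alike. Suggested content: an event belongs to the continuation phase if it starts at or after the start of that phase (control arm: pump start at Visit 9; treatment arm: Visit 9) and no later than the earlier of Visit 13 and study exit or early termination. Delete the Visit 10 limit. State that the study period ends where this interval begins, so that each event falls in exactly one period.

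For control-arm events dated on the Visit 9 day, use clock time where it is recorded. Otherwise assign them to the continuation phase, which is the conservative choice because it counts them under AHCL, and list them.

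The cost is a short SAP edit and the matching derivation. No new data should be needed: Visit 9 is the scheduled pump start, and exits are documented on the Exit eCRF (protocol 9.14). The downside is that a few events from before pump start on that day may be counted under AHCL, and the AHCL count may look slightly less favourable.
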